8.3.1.2 Enrolled Subjects

Subjects who received at least one dose of Sponsor-provided standardized GC regimen or Principal investigator-prescribed supply of GCs or were randomized.

8.3.2 Study Day

As treatment will not begin until randomization into the Treatment Period, Treatment Study Day 1 is defined as the first double-blinded dose date in the Placebo-Controlled Treatment Period. Study Day, which follows the CDISC SDTM standard, is defined as (Assessment date – date of first study drug dosing + 1 day), where the assessment date is on or after the date of first study drug dosing; (Assessment date – date of first study drug dosing), where the assessment date is before the date of first study drug dosing.

8.3.3 Enrollment Day

In this study, subjects may receive a Sponsor-provided, standardized GC regimen or Principal Investigator-prescribed supply of GCs during the 6- to 12-week Glucocorticoid Conversion Period. Enrollment Day 1 will be the first dose date of the GC regimen in the Glucocorticoid Conversion Period, following the same format as study day. For subjects who do not require the GC conversion period, enrollment day will be the same as Study Day 1

8.3.4 Tildacerfont Treatment Day

Tildacerfont Treatment Day 1 is defined as the first dose date of tildacerfont in the study, following the same format as study day. For subjects randomized into the tildacerfont treatment group in the Placebo-Controlled Treatment Period, the first dose date of tildacerfont is defined as the first double-blinded dose date in the Placebo-Controlled Treatment period. For subjects

randomized into the placebo treatment group in the Placebo-Controlled Treatment Period, the first dose date of tildacerfont is defined as the first dose date in the Open-Label Period. Tildacerfont Treatment Day will be included in select efficacy listings.

8.3.5 End of Study Treatment Definition

A subject is considered to have completed study treatment if the subject has completed all 76 weeks of the Treatment Period.

8.3.6 End of Study Definition

A subject is considered to have completed the study if the subject has completed study treatment and the follow-up visit.

8.3.7 Body Mass Index

Body mass index (kg/m^2) is derived as weight (kg) / [height (m) \times height (m)]. Height measured at Screening will be used to calculate BSA. Body mass index may be summarized using the classifications defined in [Table 6](#).

Table 6 Classification of Body Mass Index

Parameter	BMI (kg/m^2)
Underweight	< 18.8
Normal Range	18.5 -< 25
Overweight	25 -< 30
Obese Class I	30 -< 35
Obese Class II	35 - < 40
Obese Class III	≥ 40

8.3.8 Body Surface area

Body surface area (BSA) is calculated per the Mosteller formula as $\text{sqrt}((\text{height} (\text{cm}) \times \text{weight} (\text{kg})) / 3600)$. Height measured at Screening will be used in all BSA calculations.

8.3.9 Baseline Values

8.3.9.1 Baseline at Randomization

Baseline at randomization values are defined as the last non-missing assessment prior to the first dose of randomized, double-blind study drug in Placebo-Controlled Treatment Period of the study. Baseline at randomization will be used in the Primary Efficacy Endpoint, Secondary Efficacy Endpoint, and exploratory endpoint analyses that explore treatment at Week 24. Demographics and summaries of change from baseline will use baseline at randomization unless otherwise specified.

8.3.9.2 Baseline Prior to Treatment with Tildacerfont

Baseline values prior to treatment with tildacerfont are defined as the last non-missing assessment prior to the first dose of tildacerfont. For subjects randomized into the tildacerfont treatment group of the Placebo-Controlled Treatment Period, the first dose of tildacerfont is defined as the first double-blinded dose date in the Placebo-Controlled Treatment period. For subjects randomized into the placebo treatment group of the Placebo-Controlled Treatment Period, the first dose of tildacerfont is defined as the first dose in the Open-Label Period. The baseline prior to treatment with tildacerfont will be used in Secondary Efficacy and Exploratory Efficacy Endpoint analyses that explore effects after 52 weeks of tildacerfont treatment.

8.3.10 Change from Baseline

Change from baseline is calculated as the post-baseline assessment subtracted by the baseline assessment.

8.3.11 Percent Change from Baseline

Percent change from baseline is calculated as the change from baseline divided by the baseline assessment and multiplied by 100%. This value will be rounded to two decimal places unless otherwise stated.

8.3.12 Upper Limit of Normal and Targets by Efficacy Biomarker

The ULN and target values that are displayed in [Table 7](#) will be used in data analysis. The age at screening will be used to determine those age specific ULN values.

Table 7 Upper Limit of Normal Values by Subgroup and Key Biomarker

Baseline Characteristic	ACTH ULN	17-OHP ULN	17-OHP Target	A4 ULN	A4 Target (1.25xULN)
Males: 18-30	63.3 ng/dL	200 ng/dL	1200 ng/dL	220 ng/dL	275 ng/dL
Males: 31-50	63.3 ng/dL	200 ng/dL	1200 ng/dL	190 ng/dL	238 ng/dL
Males: 51+	63.3 ng/dL	200 ng/dL	1200 ng/dL	220 ng/dL	275 ng/dL
Females: pre-menopausal	63.3 ng/dL	200 ng/dL	1200 ng/dL	230 ng/dL	288 ng/dL
Females: post-menopausal	63.3 ng/dL	200 ng/dL	1200 ng/dL	75 ng/dL	94 ng/dL

8.3.13 Cardiovascular Risk Factors

CV risk factors are defined by gender in the table below. Subjects with values exceeding the threshold are considered for being at elevated risk for a CV event.

Table 8 CV Risk Factors by Gender

Risk Factor	Female	Male
HOMA-IR ^{1,2,3}	≥ 2.5	≥ 2.5
Waist circumference ^{1,4,5}	≥ 88 cm	≥ 102 cm
Total cholesterol ⁶	≥ 170 mg/dL	≥ 200 mg/dL
LDL cholesterol ⁶	≥ 110 mg/dL	≥ 130 mg/dL
Systolic blood pressure ⁷	≥ 130 mmHg	≥ 130 mmHg
Diastolic blood pressure ⁷	≥ 70 mmHg	≥ 70 mmHg
BMI ⁸	≥ 30 kg/m ² OR ≥ 27 kg/m ² and at least one other risk factor	≥ 30 kg/m ² OR ≥ 27 kg/m ² and at least one other risk factor

1 (Torkey, et al., 2021); 2 (Matthews, et al., 1985); 3 (Muniyappa, Lee, Chen, & MJ, 2008); 4 (Flint, et al., 2010); 5 (WHO, 2008); 6 (Grundy, et al., 2019); 7 (Whelton, et al., 2018); 8 (FDA, 2007)

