9.6 Type I Error Control

Type I Error control for the Secondary Efficacy Endpoints will be achieved by hierarchical testing. If the Primary Efficacy Endpoint is met, then Secondary Efficacy Endpoints displayed in [Table 5](#) will be evaluated using the Hochberg (1988) closed test procedure with an alpha of 0.05.

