12.5.1 Statistical Hypotheses for Secondary Efficacy Endpoints

For Secondary Efficacy Endpoint 2.1 the null hypothesis is that the difference between randomized treatment groups in the proportion of subjects achieving GC dose ≤ 11 mg/m²/day in HCe and A4 ≤ 1.2 times baseline or A4 \leq ULN at Week 24 is equal to zero. The alternative hypothesis is that the difference is not equal to zero.

For Secondary Efficacy Endpoint 2.2 the null hypothesis is that in the subset of subjects with a baseline GC dose ≤ 35 mg the difference between randomized treatment groups in the proportion of subjects achieving GC dose ≤ 11 mg/m²/day in HCe and A4 ≤ 1.2 times baseline or A4 \leq ULN at Week 24 is equal to zero. The alternative hypothesis is that the difference is not equal to zero.

Secondary Efficacy Endpoint 2.3 is the proportion of classic CAH subjects who were randomized into the study who improve at least one baseline CV risk factor at 24 weeks from randomization. This proportion is calculated for each treatment group (e.g., placebo, tildacerfont) as the number of subjects at Week 24 who had at least one CV risk factor at baseline (i.e. subjects without any CV risk factors will not be included in the analysis) and no longer meets one or more of the baselines CV risk factors at Week 24, divided by the total number of subjects in the ITT analysis who were randomized to that specific treatment and had at least one CV risk factor at baseline.

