12.5.1.1 Statistical Modeling and Testing

The Secondary Efficacy Endpoints are all binary ‘response’ endpoints will be analyzed using logistic regression modelling.

The model for each endpoint will include the responder indicator as the dependent variable; treatment group (0: placebo, 1: tildacerfont); the randomization strata: sex (0: male, 1: female) and baseline GC dose (in HCe, 0: < 40 mg/day, 1: ≥ 40 mg/day); and baseline GC type (0: short-acting, 1: intermediate-acting or combination) as categorical explanatory variables; and, for

Secondary Efficacy Endpoint 2.3, the baseline number of CV risk factors will also be included as a categorical covariate.

An exact score test derived from the logistic regression model, equivalent to an exact CMH test on small sample sizes, will be used to provide the 2-sided p-value to determine whether proportion of responders is different between the tildacerfont treatment group and the placebo treatment group at Week 24. If the logistic model does not converge, a Fisher's exact tests corresponding to the tildacerfont treatment group compared to placebo will be utilized.

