12.5.1.4 Supportive Analysis CV Risk Secondary Efficacy Endpoint

The responder criterion is systematically varied in order to identify the criteria under which the treatment effect is different. If Secondary Efficacy Endpoint 2.3 is significant, then each successive alternative responder definition will be tested using the methods described in [Section 12.5.1.1](#). For Endpoints 2.3A and 2.3C, subjects who are missing data required to assess CV risk factors at Week 24 will be considered to be non-responders.

Table 14 Alternate Secondary Efficacy Endpoint CV Risk Factor Responder Definitions

Def	Endpoint	Alternative Definition
2.3A	Proportion of subjects with improvement in at least 1 CV risk factor AND no worsening in a CV factor	$\begin{cases} 1 & \text{improvement in } \ge 1 \text{ baseline CV risk factor at Week 24} \\ 0 & \text{no improvement OR worsening} \end{cases}$
2.3B	Proportion of subjects with improvement in at least 2 CV risk factor	$\begin{cases} 1 & \text{no longer meets } \ge 2 \text{ baseline CV risk factor criteria at Week 24} \\ 0 & \text{no improvement} \end{cases}$
2.3C	Proportion of subjects with improvement in at least 2 CV risk factor AND no worsening in a CV factor	$\begin{cases} 1 & \text{improvement in } \ge 2 \text{ baseline CV risk factor at Week 24} \\ 0 & \text{no improvement OR worsening} \end{cases}$

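### SAP Table 8's conditional BMI factor lets the loss of one risk factor count as two improvements in supportive definitions 2.3B and 2.3C

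*SAP*

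**What the plan says.** - **Risk factors.** SAP 8.3.13, Table 8, lists seven factors: HOMA-IR, waist circumference, total cholesterol, LDL, systolic pressure, diastolic pressure and BMI. Each is a threshold: "Subjects with values exceeding the threshold are considered for being at elevated risk for a CV event". For both sexes the BMI factor is met at 30 kg/m² or more, or at 27 or more "and at least one other risk factor".
- **Improvement.** SAP 12.5.1, like Protocol 9.4.3, counts a responder on endpoint 2.3 as a subject who "no longer meets one or more of the baselines CV risk factors at Week 24". As for the denominator, "subjects without any CV risk factors will not be included in the analysis".
- **Supportive definitions.** SAP 12.5.1.4, Table 14, defines 2.3B as "Proportion of subjects with improvement in at least 2 CV risk factor", scored as two or more baseline criteria no longer met. Definition 2.3C adds that no factor has worsened. The gate is: "If Secondary Efficacy Endpoint 2.3 is significant, then each successive alternative responder definition will be tested".
- **Multiplicity.** Under SAP 9.6, once the primary endpoint is met, the secondary endpoints of Table 5 are "evaluated using the Hochberg (1988) closed test procedure with an alpha of 0.05". Endpoint 2.3 is in that family; 2.3A to 2.3C are not.
- **Covariate.** In the model for 2.3, "the baseline number of CV risk factors will also be included as a categorical covariate".
- **Measurement.** Protocol 8.2.3 has BMI calculated at every visit.

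No section fixes at baseline which BMI branch applies, requires BMI to fall before the BMI factor counts as improved, or defines worsening.

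**The concern.** Six of the seven factors stand on their own measurement. Between 27 and 30, the BMI factor also depends on whether any of the other six is present. If Table 8 is re-evaluated at Week 24, as the scoring rule implies, the BMI factor can disappear because something else disappeared, with no change in weight.

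This matters most where factors are counted. Definitions 2.3B and 2.3C ask for at least two improvements, and a reader will take them as evidence of broader benefit than 2.3. If one change can supply both counts, some of those responders are single-factor responders under another label.

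**Working it through.** The documents state no rate, power or sample size for endpoint 2.3 or for Table 14, so there is no figure to reproduce. The check is logical.

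**Rule applied.** The BMI factor is met if BMI ≥30, or if BMI ≥27 and at least one of the other six factors is present. The alternative grouping, in which even BMI ≥30 needs another factor, would make the 30 limb redundant. An improvement is a criterion met at baseline and not met at Week 24.

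**Worked cases.** Systolic pressure (threshold 130 mmHg) is the example of the other factor; a loss could be 132 to 128 mmHg.

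| BMI, baseline to Week 24 | Other factors | Factors, baseline to Week 24 | Improvements |
|---|---|---|---|
| 28 to 28 | systolic only, lost | 2 to 0 | 2 |
| 28 to 29.9 | systolic only, lost | 2 to 0 | 2 |
| 31 to 31 | systolic only, lost | 2 to 1 | 1 |
| 26 to 26 | systolic only, lost | 1 to 0 | 1 |
| 28 to 28 | systolic lost, diastolic kept | 3 to 2 | 1 |
| 28 to 28 | systolic lost, diastolic gained | 2 to 2 | 1 |

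The same change in systolic pressure scores two only in the conditional BMI band, and only when no other factor is left at Week 24. In the second row BMI has gone up and is still scored as improved.

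**Enumeration.** BMI was held at 28, and all 64 × 64 baseline and Week 24 patterns of the other six factors were scored.

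- The spurious BMI improvement appears in 63 patterns. These are exactly the patterns with at least one other factor at baseline and none at Week 24: 2⁶ − 1 = 63.
- It changes 2.3 status in 0 of them. It can arise only when another factor has really been lost, and that loss already makes the subject a 2.3 responder. Endpoint 3.5 uses the same criterion at Week 52, so the same holds there.
- It changes at-least-two status (2.3B) in 6 patterns, one for each factor that can be the sole other factor. In the other 63 − 6 = 57, two or more other factors were lost, so the subject qualifies without BMI.

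**Mirror case.** A subject at BMI 28 with no other factor who gains one goes from 0 to 2 factors. That subject has no baseline factor and is outside the analysis, so this direction does no harm here.

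These are counts of possible patterns, not of subjects.

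**The case against.** **Reach.** The double count never touches a multiplicity-controlled endpoint. Definitions 2.3B and 2.3C are supportive and are tested only after 2.3 is significant. The rule is also the same in both arms, so it does not by itself create a treatment difference. All of this stands, and it limits the point to what a 2.3B or 2.3C response means.

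**Narrowness.** The subject needs exactly one of six other factors. With systolic pressure as that factor, diastolic pressure must be below 70 mmHg, HOMA-IR below 2.5, and waist, total cholesterol and LDL all below their limits. The low diastolic threshold in particular makes a sole other factor less likely. The result is also not automatic: at a Week 24 BMI of 30 or more, the BMI factor is still met and only one improvement is scored. This stands too.

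**Definition 2.3C.** Worsening is undefined, so a rise from 28.0 to 29.5 might disqualify the subject there. A 2.3C response is therefore conditional.

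**Consistency with Table 8.** A subject at BMI 28 with no other factor does not have the BMI factor, so scoring it as lost follows the text. That is right as a classification at one visit. It does not justify counting one measured change twice in a definition that asks for two improvements.

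**A stronger reading.** A reader might infer that Table 8 also errs when BMI falls from 31 to 28 while another factor persists, because no BMI improvement is scored, whereas the same fall with no other factor is credited. The documents do not support calling this an error. The subject still meets Table 8 at Week 24, so the score follows SAP 12.5.1 exactly and nothing is counted twice. Crediting that fall would contradict the no-longer-met rule. It would also set a new unequal hurdle among subjects with a persisting factor: (30.5 − 30)/30.5 = 1.6% from a baseline of 30.5, against (29.9 − 27)/29.9 = 9.7% from 29.9. Response rates, including for 2.3, could rise. BMI and waist circumference changes are analysed directly in exploratory endpoints 3.10 and 3.12.

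**Conclusion.** The point holds for 2.3B, and for 2.3C if no factor is judged to have worsened. A subject with BMI 27 to <30 and exactly one other baseline factor, who loses it, gains none and stays at BMI 27 to <30, is scored as improved on two factors after one real change. For such subjects the two definitions repeat the single-factor result.

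A reader might infer that endpoint 2.3 or 3.5 is distorted by this double count; the enumeration shows it cannot be. A reader might also want a figure in percentage points. The documents give neither the share of subjects with this baseline pattern nor the rate at which they lose the other factor, so no estimate is offered.

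The conclusion assumes that Table 8 is re-evaluated in full at Week 24, which is the plain reading of SAP 12.5.1. The defect is real and cheap to remove, and it is confined to supportive analyses.

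**What to change.** Keep Table 8 unchanged for baseline classification. Add to SAP 8.3.13, with a cross-reference in Table 14: where the baseline BMI factor was met through the 27 to <30 branch, it counts as improved only if BMI is below 27 at the assessment visit; losing the other factor alone is not a BMI improvement.

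Under this rule, BMI 28 unchanged with systolic pressure lost gives one improvement and is no longer a 2.3B response. BMI 28 to 26.5 with systolic pressure lost still gives two. The 2.3 denominator, the baseline factor-count covariate and the results of 2.3 and 3.5 do not change.

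The cost is one sentence, a cross-reference and one derived flag, with no new data. The downside is that 2.3B and 2.3C response rates may be slightly lower.

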8.3.14 Responder Definitions

Where Efficacy Endpoints are proportions of responders based on serum hormone assessments, GC dose, and/or CV risk factors, indicator variables will be created as [Table 9](#).

Table 9 Responder Definition by Endpoint

Endpoint	Definition
Proportion of subjects with GC dose ≤ 11 mg/m ² /day in HCe and A4 $\leq 1.2 \times$ baseline or A4 \leq ULN at Week 24	$1 = \text{Week 24 GC dose} \leq 11 \text{mg/m}^2/\text{day in HCe AND (A4} \leq 1.2 \times \text{baseline or A4} \leq \text{ULN})$ $0 = \text{otherwise}$
Proportion of subjects with baseline GC dose ≤ 35 mg HCe who achieve GC dose ≤ 11 mg/m ² /day in HCe and A4 $\leq 1.2 \times$ baseline or A4 \leq ULN at Week 24	$1 = \text{Baseline GC dose} \leq 35 \text{mg HCe AND Week 24 GC dose} \leq 11 \text{mg/m}^2/\text{day in HCe AND (A4} \leq 1.2 \times \text{baseline or A4} \leq \text{ULN})$ $0 = \text{otherwise}$
Proportion of subjects with GC dose ≤ 11 mg/m ² /day in HCe and A4 $\leq 1.2 \times$ baseline or A4 \leq ULN at Week 52	$1 = \text{Week 52 GC dose} \leq 11 \text{mg/m}^2/\text{day in HCe AND (A4} \leq 1.2 \times \text{baseline or A4} \leq \text{ULN})$ $0 = \text{otherwise}$
Proportion of subjects with baseline GC dose ≤ 35 mg HCe who achieve GC dose ≤ 11 mg/m ² /day in HCe and A4 $\leq 1.2 \times$ baseline or A4 \leq ULN at Week 52	$1 = \text{Baseline GC dose} \leq 35 \text{mg HCe AND Week 52 GC dose} \leq 11 \text{mg/m}^2/\text{day in HCe AND (A4} \leq 1.2 \times \text{baseline or A4} \leq \text{ULN})$ $0 = \text{otherwise}$
Proportion of subjects with at least a 5 mg/day HCe reduction from baseline (Day 1) in GC dose and A4 $\leq 1.2 \times$ baseline or \leq ULN at week 24	$1 = \text{Week 24 GC dose reduction from baseline} \leq -5 \text{mg/day in HCe AND (A4} \leq 1.2 \times \text{baseline or A4} \leq \text{ULN})$ $0 = \text{otherwise}$
Proportion of subjects with at least a 5 mg/day HCe reduction from baseline (Day 1) in GC dose and A4 $\leq 1.2 \times$ baseline or \leq ULN at week 52	$1 = \text{Week 52 GC dose reduction from baseline} \leq -5 \text{mg/day in HCe AND (A4} \leq 1.2 \times \text{baseline or A4} \leq \text{ULN})$ $0 = \text{otherwise}$
Proportion of subjects with ≥ 1 CV risk factor at baseline achieving an improvement in at least one CV risk factor at Week 24	$\begin{cases} 1 & \text{improvement in } \geq 1 \text{ baseline CV risk factor at Week 24} \\ 0 & \text{no improvement} \end{cases}$
Proportion of subjects with ≥ 1 CV risk factor at baseline achieving an improvement in at least one CV risk factor at Week 52	$\begin{cases} 1 & \text{improvement in } \geq 1 \text{ baseline CV risk factor at Week 52} \\ 0 & \text{no improvement} \end{cases}$

8.3.15 Quality of Life Assessments and Scoring

8.3.15.1 HADS Anxiety and Depression Scores

The scale consists of 14 items, 7 items each for anxiety and depression. The anxiety score is the sum of the odd-numbered items (questions 1, 3, 5, 7, 9, 11, 13), and the depression score is the sum of the even-numbered items (questions 2, 4, 6, 8, 10, 12, 14). Each item is rated on a 4-point scale based on the frequency of symptoms over the preceding week and ranging from 0 (not at all) to 3 (very often). The sub-scores are the sum of individual item scores within each subcategory (anxiety or depression) and ranges from 0 to 21, with higher scores corresponding to higher levels of anxiety or depression. The total score of the individual item scores and ranges from 0 to 42, with higher scores corresponding to higher levels of anxiety or depression.

8.3.15.2 SF-36 Domain Scores and Component Scores

The SF-36 consists of 36 items in the following 8 domains: physical functioning, physical role functioning (limitations in usual role activities because of physical health problems), bodily pain, general health perceptions, vitality, social functioning, emotional role functioning (limitations in usual role activities because of emotional problems), and mental health; these domain scores are abbreviated PF, RP, BP, GH, VT, SF, RE, MH respectively. Domain scores range from 0 to 100, with higher scores corresponding to better subjective health status; these are then normalized to scores obtained in the 2009-general population, such that scores above 50 are higher than the general population and scores less than 50 are lower than those for the general population. In addition, and overall component score representing physical functioning (PCS) and mental functioning (MCS) are calculated, which are also normalized to the general population. The SF-36 scores will be calculated and provided by Medpace Reference Laboratories.

8.3.15.3 Patient Global Impression of Change and Clinical Global Impression – Improvement (PGIC)

The PGIC is a 1-question survey that asks subjects to evaluate whether there has been an improvement in overall subjective health status. Subjects select a response on a 7-point Likert scale. The CGI-I is a 1-question survey that requires the clinician to assess how much a patient's

illness has improved or worsened relative to a baseline state. Clinicians select a response on a 7-point Likert scale.

